For the product of the ratio of average glucose (Week 12/Baseline) and ratio of average insulin use (Week 12/Baseline), glucose AUC after MMTT, C-peptide AUC after MMTT and arginine challenge test (for a subset of subjects in Part A who were enrolled prior to Protocol Amendment #1), fasting glucose, insulin, C-peptide, GLP-1, and glucagon, a repeated measures analysis of covariance will be performed, as well as before and after treatment analysis.

For comparison of proportion of subjects that achieve HbA1c reduction of $\geq 0.4\%$ in the REMD-477 and placebo groups, chi-square test will be conducted.

For a subset of subjects in Part B, the change in hepatic fat content from baseline will be calculated for each subject and the mean change will be calculated for each treatment arm.

Study Disposition and Demographic Data

The number of subjects who receive investigational product and complete the study will be summarized. A list of subjects who withdraw early will be provided. It will include the reason and timing of the withdrawal. Similarly, the reason any subject is excluded from an analysis set will also be provided. In addition, significant known protocol deviations will be noted for individual subjects.

Age, race, sex, height, and weight will be summarized for all the subjects receiving investigational product using descriptive statistics.

Population Pharmacokinetics

Serum REMD-477 concentrations will be determined using a validated assay. A population

PK analysis will be performed from REMD-477 concentrations evaluated on Days 1, 8, 29, 57, 85, and 106.

Safety Analysis

Adverse Events

All subjects who receive at least one dose of REMD-477 or placebo will be included in the safety analyses. The number of subjects reporting treatment-emergent adverse events will be determined overall, by preferred term, and by system organ class according to the current MedDRA terminology. The number and percentage of subjects reporting adverse events will be evaluated for each treatment and will also be tabulated by relationship to study drug.

Adverse events resulting in treatment discontinuation will be identified.

Vital Signs

Vital signs will be listed and reviewed for each subject. Summaries of heart rate and blood pressure data over time and change from baseline will be provided. Depending on the size and scope of change in other vital signs, summaries may be provided for this data.

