5.2 Secondary Objectives

- To compare the effects of multiple doses of REMD-477 versus placebo on measures of glycemic control including change from baseline at Week 13 in fasting glucose and glucose area under the curve (AUC) after mixed meal tolerance test (MMTT) – Part A only.
- To compare the effects of multiple doses of REMD-477 versus placebo on change from baseline at Week 12 in average daily 24-h blood glucose concentration and time within target range as assessed by continuous glucose monitoring (CGM) and seven-point glucose profile.

- To compare the effects of multiple doses of REMD-477 versus placebo on the product of the ratio of average glucose (Week 12/Baseline) and ratio of average insulin use (Week 12/Baseline).
- To evaluate the safety and tolerability of multiple doses of REMD-477 versus placebo.
- To compare the incidence of hypoglycemic episodes after multiple doses of REMD-477 versus placebo.
- To compare the effects of multiple doses of REMD-477 versus placebo on change from baseline at Week 13 in hemoglobin A1c (HbA1c).
- To compare the proportion of subjects who achieve HbA1c reduction of $\geq 0.4\%$ after multiple doses of REMD-477 versus placebo at Week 13.
- To compare the effects of multiple doses of REMD-477 versus placebo on pancreatic beta cell function as measured by change from baseline at Week 13 in C-peptide AUC after a MMTT and arginine challenge test (for a subset of subjects who were enrolled prior to Protocol Amendment #1) – Part A only.
- To compare the effects of multiple doses of REMD-477 versus placebo on pancreatic alpha cell function as measured by change from baseline at Week 13 in peripheral levels of fasting glucagon, active and total glucagon-like peptide 1 (GLP-1), and glucagon and GLP-1 (active and total) AUC after MMTT – Part A only.
- To determine REMD-477 plasma concentrations and formation of anti-REMD-477 antibodies after multiple dosing.

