10 STATISTICAL METHODOLOGY

10.1 General

Data listings will be provided for the All Subjects Population. Summary statistics and statistical analyses will be performed for subjects included in the relevant analysis populations (Safety/PK/PD).

For continuous data, summary statistics will include the arithmetic mean, arithmetic standard deviation, median, minimum, maximum, and number. For log-normal data (eg, the Mixed Meal Tolerance Test [MMTT] parameters: areas under the concentration-time curve [AUCs]), the geometric mean and geometric coefficient of variation (CV%) will also be presented. For categorical data, frequency counts and percentages will be presented. Data listings will be provided for all subjects. For the calculation of summary statistics and statistical analysis, unrounded data will be used.

Outputs will be created separately for Parts A and B.

Missing values will not be imputed.

Data analysis will be performed using SAS® Version 9.4.

Analysis Data Model (ADaM) datasets will be prepared using Clinical Data Interchange Standards Consortium (CDISC) ADaM Version 2.1, and CDISC ADaM Implementation Guide Version 1.1. Pinnacle 21 Community Validator Version 2.2.0 will be utilized to ensure compliance with CDISC standards.

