10.1.1 Definition of Baseline and Change from Baseline

Unless otherwise stated, the baseline for each parameter is defined as the last value measured prior to first dosing, including repeat (vital signs and electrocardiograms [ECGs]) and unscheduled (clinical laboratory parameters) readings (see Section 10.1.2 for definitions of repeat and unscheduled readings). For ECGs taken in triplicate, baseline will be the mean of the last three values taken prior to first dosing.

Mean change from baseline is the mean of all individual subjects' change from baseline values. Each individual change from baseline will be calculated by subtracting the individual subject's baseline value from the value at the timepoint. The individual subject's change from baseline values will be used to calculate the mean change from baseline using a SAS procedure such as Proc Univariate.

Mean percent change from baseline is the mean of all individual subjects' percent change from baseline values. Each percent change from baseline will be calculated by subtracting the individual subject's baseline value from the value at the desired timepoint and then dividing this calculated value by the individual subject's baseline value and multiplying by 100. These individual subjects' percent changes from baseline values will be used to calculate the mean percent change from baseline using a SAS procedure such as Proc Univariate.

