10.3.2 Secondary Pharmacodynamic Endpoints

- Change from baseline at Week 13 in fasting glucose and glucose AUC after the MMTT – Part A only.
- Change from baseline at Week 12 in average daily 24-h blood glucose concentration and time within target range as assessed by CGM and seven-point glucose profile.
- The product of the ratio of average glucose (Week 12/Baseline) and ratio of average insulin use (Week 12/Baseline).
- Change from baseline at Day 85 (Week 13) in HbA1c.
- Proportion of subjects who achieve HbA1c reduction of $\geq 0.4\%$.
- Change from baseline at Day 85 (Week 13) in fasting C-peptide and C-peptide AUC after MMTT and arginine challenge (for a subset of subjects who were enrolled prior to Protocol Amendment #1) – in Part A only.
- Change from baseline at Day 85 (Week 13) in peripheral levels of fasting glucagon, active and total GLP-1, and glucagon and GLP-1 (active and total) AUC after MMTT challenge – in Part A only.

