10.3.4.6 HbA1c

The HbA1c concentrations will be summarized separately for Parts A and B by treatment group and timepoint, along with changes from baseline. The baseline assessment for Part A subjects is defined as the measurement taken at the Lead-In (OBV) period for those subjects enrolled prior to Amendment # 1 of the protocol or the baseline visit for those thereafter. For subjects enrolled in Part B the baseline assessment is defined as the last assessment taken prior to Day 1 dosing..

The changes from baseline for HbA1c will be statistical analyzed separately for Parts A and B. A repeated measures ANCOVA will be used to compare changes between treatment groups for each timepoint. Dependent variables will be treatment, day, and the treatment by day interaction. The baseline variable will be used as a covariate. Covariates may be added to the above model depending on the results from the comparison of baseline characteristics as detailed in section [10.3.4.1](#).

Subject will be used as a random effect. The LS mean for each treatment will be presented for each timepoint. Also, the difference from placebo, the 95% CI of the difference from placebo, and p-value associated with the null-hypothesis of no difference will be reported for each timepoint.

The number and proportion of subjects who achieve HbA1c reduction of $\geq 0.4\%$ will be summarized separately for Parts A and B by timepoint and treatment group. Reduction of $\geq 0.4\%$ is defined by the occurrence of a change from baseline which is less than -0.4% . A chi-square test will be conducted to compare the frequency observed in each of the two REMD-477 treatment groups versus the placebo group at each post-baseline timepoint.

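### SAP 10.3.4.6 codes the HbA1c responder endpoint (reduction of at least 0.4%) with a strict cut-off, so a drop of exactly 0.4 meets the endpoint but fails the rule; small effect, easy fix

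*SAP*

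**What the plan says.** The endpoint is inclusive wherever it is named. SAP 5.2 has the objective "To compare the proportion of subjects who achieve HbA1c reduction of" ≥0.4% at Week 13, and SAP 10.3.2 lists "Proportion of subjects who achieve HbA1c reduction of" ≥0.4%. The protocol synopsis, its objectives and its Section 10 agree; the analysis text there begins "For comparison of proportion of subjects that achieve HbA1c reduction of" ≥0.4%.

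SAP 10.3.4.6 opens its responder paragraph the same way: "The number and proportion of subjects who achieve HbA1c reduction of" ≥0.4% will be summarised by Part, timepoint and treatment. The next sentence gives the derivation: such a reduction "is defined by the occurrence of a change from baseline which is less than" −0.4%. The result is then tested: "A chi-square test will be conducted to compare the frequency observed in each of the two REMD-477 treatment groups versus the placebo group". This is repeated for every visit after baseline.

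Two general rules bear on this. SAP 10.1.1 fixes the sign: "Each individual change from baseline will be calculated by subtracting the individual" subject's baseline from the timepoint value, so a fall is negative. SAP 10.1 states: "For the calculation of summary statistics and statistical analysis, unrounded data will be used". SAP Section 12, which lists departures from the protocol's analyses, does not mention the responder cut-off.

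**The concern.** The sentence in SAP 10.3.4.6 is the only operational definition of the responder, and SAP Section 4 says that the SAP supersedes the protocol's statistical considerations. A programmer who follows it would code a strict inequality. The reported proportions and the chi-square tests would then not be exactly those of the stated endpoint, although the tables would probably carry the ≥0.4% label. Since the inclusive form is repeated everywhere else, this reads as a drafting slip and not as a deliberate change.

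There is a second, linked weakness. HbA1c is reported on a coarse grid, so ties at exactly 0.4 can be common, and the SAP does not say how a tie is to be evaluated. The counts would depend on whether the programmer rounds. With about 25 subjects per arm, each reclassified subject moves a reported proportion by 4 points (1/25).

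**Working it through.** **1. The boundary case.** For a fall of exactly 0.4, the endpoint asks whether 0.4 ≥ 0.4, which is true. The derivation asks whether −0.4 < −0.4, which is false. This needs no assumption.

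**2. Inputs.** From the documents: 25 subjects per group in each Part (SAP Section 8), and screening HbA1c above 7% and below 10% (protocol inclusion criteria). The documents give no responder rate, power or sample size for this endpoint, so there is no stated figure to reproduce. They also do not give the HbA1c reporting precision or the SD and mean of the change. Assumed: normal change, SD 0.4 to 0.8, mean 0 to −0.8, reporting to 0.1 or to 0.01.

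**3. How a tie computes on unrounded data.** In double precision, 7.6 − 8.0 gives −0.40000000000000036, which passes. But 7.2 − 7.6 gives −0.39999999999999947, which fails. Running every baseline on the grid with a true drop of 0.4:

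| Baselines | Pass under < | Pass under ≤ | Fail under both |
|---|---|---|---|
| 7.1 to 9.9, step 0.1 | 20 of 29 | 20 of 29 | 9 of 29 (31%) |
| 6.0 to 11.0, step 0.1 | 36 of 51 | 36 of 51 | 15 of 51 (29%) |
| 7.01 to 9.99, step 0.01 | 209 of 299 | 209 of 299 | 90 of 299 (30%) |
| 7.1 to 9.9, change rounded to 0.1 | 0 of 29 | 29 of 29 | none |

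The nine failing baselines in the first row are 7.1, 7.3, 7.6, 7.8, 8.1, 8.2, 8.7, 9.2 and 9.7. The 6.0 to 11.0 row is included because the analysis baseline is taken after screening and need not stay within the eligibility range.

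**4. How many subjects sit on the boundary.** With reporting step g, mean μ and SD σ:

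P(tie) = Φ((−0.4 + g/2 − μ)/σ) − Φ((−0.4 − g/2 − μ)/σ)

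- g = 0.1: from 0.0440 (σ = 0.8, μ = 0) to 0.0995 (σ = 0.4, μ = −0.4).
- g = 0.01: from 0.0044 to 0.0100.

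**5. Responders lost = failing share × P(tie).**

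- Unrounded, one decimal, baselines spread evenly over 7.1 to 9.9: 9/29 × (0.0440 to 0.0995) = 1.4% to 3.1%, or 0.3 to 0.8 of 25 per arm.
- The same over 6.0 to 11.0: 15/51 × (0.0440 to 0.0995) = 1.3% to 2.9%.
- The same with normal baselines (mean 7.4 to 8.6, SD 0.5 to 0.9): failing share 27% to 40%, loss 1.2% to 4.0%, or 0.3 to 1.0 of 25.
- Unrounded, two decimals: 90/299 × (0.0044 to 0.0100) = 0.13% to 0.30%, or 0.03 to 0.08 of 25.
- Change rounded to one decimal, then tested strictly: every tie is lost, 4.4% to 9.9%, or 1.1 to 2.5 of 25.

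**6. Effect on the comparison with placebo.** The difference in proportions shifts by −share × [P(tie, active) − P(tie, placebo)]. Placebo means were taken from 0 to −0.3 and active means from −0.2 to −0.8. For one decimal and σ = 0.4:

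- Placebo 0, active −0.4: −(0.0995 − 0.0605) = −3.9 points if rounded and strict; × 9/29 = −1.2 points if unrounded.
- Placebo −0.3, active −0.8: −(0.0605 − 0.0964) = +3.6 points if rounded and strict; × 9/29 = +1.1 points if unrounded.

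These are the extremes over the grid with evenly spread baselines. Normal baselines widen the unrounded range to −1.6 to +1.4 points. Two-decimal unrounded data keep it within ±0.12.

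**7. Power.** Two binomials of 25 were enumerated exactly, using a Pearson chi-square without correction at two-sided 0.05 (sidedness assumed), and compared with the inclusive rule. Unrounded one-decimal data change power by −2.1 points (0.667 to 0.646, at σ = 0.4, means 0 and −0.35) to +0.9 points. Rounded and strict, the change is −5.3 to +3.3 points.

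**The case against.** The strongest reply is that, on unrounded data, the faulty word has no numerical effect. No tie computes to exactly −0.4 on the one-decimal grid from 6.0 to 11.0, so strict and inclusive operators give the same counts. The unrounded losses come from binary subtraction and would remain if the SAP already said 'less than or equal to'. That is correct. The operator by itself matters only if changes are rounded, which is the 1.1 to 2.5 of 25 case. It is also why correcting the operator alone is not a sufficient remedy.

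It can further be said that a SAP seldom specifies floating-point handling, that the unrounded-data rule may be meant only to stop rounding for display before summaries are computed, and that storage, precision and code are not described. This limits how firmly one can predict what the program will do. It does not remove the contradiction between the endpoint and its derivation.

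Finally, this is one of many secondary endpoints, outside the Hochberg procedure, and a careful programmer may query the mismatch. That supports calling the effect small. It does not support leaving a wrong threshold rule in the document that governs the analysis.

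**Conclusion.** The concern holds. The only operational rule for this secondary endpoint contradicts the endpoint at its boundary, and the SAP does not declare a change. The textual contradiction is certain. Its size is not, because it rests on assumed HbA1c precision, distribution of change and baseline distribution.

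Under those assumptions the effect is small: up to about 1 subject of 25 per arm on unrounded one-decimal data, 1.1 to 2.5 if changes are rounded and tested strictly, and negligible on unrounded two-decimal data. The direction of the shift in the treatment difference depends on where each arm's mean change lies relative to −0.4, so it cannot be called conservative or anti-conservative in advance. Only the responder proportions and their chi-square tests are affected. The correction should be made because it is nearly free and belongs before database lock, when it cannot be influenced by results.

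**What to change.** In SAP 10.3.4.6, define a responder as a subject whose change from baseline in HbA1c is less than or equal to −0.4%, evaluated after rounding the change to the precision at which the laboratory reports HbA1c. State that precision. Add a short clause making this an explicit exception to the unrounded-data rule in SAP 10.1, so that the two sections do not conflict. The rounding step is needed as well as the operator: with both, all 29 one-decimal ties from 7.1 to 9.9 are counted as responders.

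The cost is one operator, one rounding statement with its exception, and one precision value to obtain from the laboratory. No new data are needed, and sample size and alpha do not change.

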10.3.4.7 Serum Ketones and Free Fatty Acids

The serum ketones and free fatty acids concentrations will be summarized by treatment group and timepoint, along with its changes from baseline. The baseline value for subjects in Part A enrolled prior to protocol amendment #1 is the average value between the Lead-In (OBV) period and Day 1 pre-dose. For all other subjects the baseline value is the last assessment taken prior to Day 1 dosing

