After the Lead-in Period (which includes the completion of the two week CGM period), eligible subjects will be admitted to the CRU around 4:00 pm for a single overnight stay on one of the following study days: Day -8, -7, -6, -5, -4, -3, or -2 relative to the subject's scheduled dosing day (Day 1). The OBV must be performed within 8 days (check-in to occur between Day -8 to Day -2) prior to administration of study drug.

At the time of admission, data from the DexCom CGM device, the subject's diary capturing insulin use, and the seven-point glucose measurements will be obtained and reviewed. CGM results from the study DexCom device will be downloaded and typical measures of glycemic control (mean glucose, standard deviation, time in range) will be recorded. CGM results will be unblinded throughout the study.

Additionally, the following baseline assessments will be completed: medical history, physical exam, body weight, urine pregnancy test, urine drug and alcohol test, 12-lead ECG, and vital signs, per the Schedule of Assessments. Safety and PD labs, including serum chemistry, hematology, urinalysis, HbA1c, insulin, C-peptide, glucagon, serum ketones, free fatty acids (FFA), and GLP-1 will be collected. Fasting plasma glucose samples will be collected on the following morning, prior to the administration of the MMTT and Arginine Challenge Tests. During the 8 hour overnight fast, plasma glucose via YSI will be measured hourly, and subjects will be allowed to receive juice by mouth, in case of hypoglycemia.

For subjects on insulin pumps: Subjects will be admitted to the CRU at approximately 1600 (4:00 pm). A peripheral IV will be placed at this time. They will be given a standard dinner at 1800 (6:00 pm) for which they can bolus as they normally would via their insulin pump for that particular meal. At approximately 1900 (7:00 pm), the subject's insulin pump will be disconnected and suspended and IV insulin infusion will begin. Blood glucose control will be maintained per [Appendix C](#) to maintain euglycemia in the 90-120 mg/dl range with start rates

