For subjects on insulin pumps: Subjects will be admitted to the CRU at approximately 1600 (4:00 pm). A peripheral IV will be placed at this time. They will be given a standard dinner at 1800 (6:00 pm) for which they can bolus as they normally would via their insulin pump for that

particular meal. At approximately 1900 (7:00 pm), the subjects insulin pump will be disconnected and suspended and IV insulin infusion will begin. Blood glucose control will be maintained per [Appendix C](#) to maintain euglycemia in the 90-120 mg/dl range with start rates described in also in [Appendix C](#). The MMTT and arginine challenge will then be performed the next morning at approximately 8:00 am [please note: the insulin infusion will continue until the completion of the both the MMTT and Arginine challenge Test assessments]. After completing the 2 hour MMTT, subjects will be administered an arginine challenge test. During both challenge tests, C-peptide, glucagon, insulin, GLP-1, and glucose concentrations will be measured. Stimulated C-peptide will be measured with the ultra-sensitive C-peptide kit from Mercodia. Upon completion of all tests, subjects may be given additional insulin via SC injection or a bolus of insulin via either IV or insulin pump, at the discretion of the investigator. Additionally, the subject's insulin pump will be restarted immediately after completion of all tests. Subjects will be monitored closely by CGM and YSI as needed and discharged only after blood glucose is < 250mg/dl and relatively stable (not rapidly declining).

For subjects on insulin injections with basal insulin given at night: Subjects can take their last dose of long acting insulin 1 day prior to admission in the evening. They will be admitted and be administered SC or bolus insulin as they would with their rapid acting injection for dinner. Insulin infusion via IV will start at 7:00 pm. No basal insulin injection will be given SC on the night of admission. After all study procedures have been completed the next morning, subjects may receive additional insulin via SC injection or a bolus of insulin via IV, at the discretion of the investigator. At that time they should take half their normal dose of basal insulin SC. They can take the second half at their usual time later that evening. The following day, they can resume their full, normal basal insulin dose.

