Mean corpuscular hemoglobin (MCH)
corpuscular hemoglobin concentration (MCHC)
count
RDW

White blood cells (WBC)
Differential count:
• Segmented neutrophils
• Band cells
• Eosinophils Mean
• Basophils Platelet
• Lymphocytes
• Atypical lymphocytes

Miscellaneous

Serum Ketones
Free Fatty Acids

Urinalysis

Specific gravity	pH
Blood	Protein
Glucose	Ketones
Bilirubin	Urobilinogen
WBC	RBC
Epithelial Cells	Bacteria
Casts	Crystals

Urine Drug Test

Amphetamine	Cocaine
Opiates	Benzodiazepines
Barbiturates	Methadone
	Alcohol/Ethanol

Other Screening Laboratory Tests

At screening, a spot urine collection will be evaluated for presence of alcohol and drugs of abuse listed above. Urine will also be collected at the Baseline Visit, Day 29, and Day 162 and will be evaluated for the analytes listed above (urine drug test). The results will be documented in the source records, but not captured on the respective eCRF page.

Next, serum will be collected for a follicle stimulating hormone (FSH) test (for women who are at least 1 year postmenopausal) at screening. Women of non-childbearing potential must have FSH levels ≥ 40 IU/mL.

Other Serum Laboratory Testing

Blood samples to measure GLP-1, glucagon, HbA1c, plasma insulin, serum ketones, free fatty acids (FAA), and C-peptide will be obtained after an overnight fast of 8 hours, or at time points outlined in the Schedule of Assessment ([Appendix A](#)). Please refer to laboratory

manual for detailed collection, handling and shipping procedures for GLP-1, glucagon, serum ketones, FFA, insulin and C-peptide samples.

Anti-REMD-477 Antibody sample collection

Subjects will have blood samples drawn for antibody determination on Days 1 (pre-dose), 85, and 162/EOS.

Sample collection, serum processing, and shipping instructions will be provided in a separate lab manual.

Blood Collection for Serum Pharmacokinetics Analysis

Blood will be collected and assayed for REMD-477 serum concentration. Baseline measurements will be collected just before dosing on Day 1. Samples will be drawn on Days 1, 8, 29, 57, 85, and 106. If a sample draw occurs during a dosing day, the sample should be collected pre-dose. Time of PK sample collection will be recorded in hours and minutes.

Sample collection, processing, storage and shipping instructions will be provided in a separate lab manual.

Exploratory Biomarker Collection

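### Part A uses two baseline definitions for serum ketones and free fatty acids, so the pooled changes from baseline are not on one footing

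*SAP*

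**What the plan says.** SAP 10.3.4.7 gives two rules for one variable. The baseline for Part A subjects "enrolled prior to protocol amendment #1 is the average value between the Lead-In (OBV) period and Day 1 pre-dose". The next sentence adds: "For all other subjects the baseline value is the last assessment taken prior to Day 1 dosing". The section gives no reason for the difference.

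The general rule in SAP 10.1.1 is: "Unless otherwise stated, the baseline for each parameter is defined as the last value measured prior to first dosing". Its opening words permit exceptions, so 10.3.4.7 departs from the default but does not contradict it.

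The planned use is descriptive: "The serum ketones and free fatty acids concentrations will be summarized by treatment group and timepoint, along with its changes from baseline". No model, confidence interval or test is specified. Under SAP 10.1, Parts A and B are reported separately, so the two rules meet only inside the Part A output.

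At the OBV, subjects are admitted at about 4 pm and intravenous insulin starts at about 7 pm. For pump users the pump is "disconnected and suspended and IV insulin infusion will begin". The visit text lists the laboratory samples together ("HbA1c, insulin, C-peptide, glucagon, serum ketones, free fatty acids (FFA), and GLP-1 will be collected") with no clock time. It places only fasting plasma glucose on the following morning. Protocol section 7, under Other Serum Laboratory Testing, says these samples "will be obtained after an overnight fast of 8 hours", but the same sentence then allows the schedule's time points as an alternative.

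**The concern.** A change from baseline can be read across subjects only if baseline means the same thing for each of them. Here, within one arm of Part A, it means a two-sample mean for some subjects and a single value for others, and enrolment date decides which.

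The reason for the split is hard to see. Later Part A enrollees also have two pre-dose samples, at the Baseline Visit and on Day 1, and theirs are not averaged, so noise reduction does not explain the rule. Averaging is confined to the subjects whose two samples were taken under unlike conditions.

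The variable matters because the trial aims to reduce insulin use and its procedures warn subjects about ketoacidosis. Finger-stick ketones are only listed (SAP 10.3.4.9), and urinalysis values are only flagged on listings (SAP 10.4.2). Serum ketones are therefore the only ketone measure that the SAP summarizes by arm.

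**Working it through.** The plan states no figure on this point, so there is none to reproduce. The check has two steps: sampling conditions, then algebra.

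**1. Are the averaged samples alike?**

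- Early enrollees, OBV, if drawn with the admission labs: about 4 pm, not after an overnight fast, and before the infusion.
- Early enrollees, OBV, if drawn next morning: fasted, but on intravenous insulin titrated to 90–120 mg/dL (protocol Appendix C).
- Day 1 pre-dose and weekly dosing visits: Appendix A pairs the ketone and fatty acid sample with a plasma glucose after at least 8 hours' fast, on the subject's own insulin regimen.
- Later Part A enrollees, Baseline Visit: after an 8-hour fast at home, on the usual regimen.

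On either reading, the OBV sample differs in condition from Day 1. For later enrollees the two samples are alike.

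The closest comparator in the SAP is fasting glucose. Appendix A schedules it at the same two pre-dose visits, and SAP 10.3.4.3 takes the last value before the first dose, with no averaging.

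**2. What does the mixed rule do to the summary?**

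Let δ be the OBV value minus the Day 1 pre-dose value, and f the share of early enrollees in an arm.

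- Early enrollee's baseline: Day 1 + δ/2, so the change shifts by −δ/2.
- Arm mean change: shifts by −f·δ/2.
- Difference from placebo: shifts by −(f_active − f_placebo)·δ/2.

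Both δ and f are missing from the documents. The table assumes values of each, with δ in any unit, for example as a fraction of the Day 1 level. Entries are the shift in arm mean change.

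| δ (assumed) | f = 0.1 | f = 0.5 | f = 0.9 |
|---|---|---|---|
| −0.3 | +0.015 | +0.075 | +0.135 |
| −0.1 | +0.005 | +0.025 | +0.045 |
| 0 | 0 | 0 | 0 |
| +0.1 | −0.005 | −0.025 | −0.045 |
| +0.3 | −0.015 | −0.075 | −0.135 |

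For example, δ = −0.3 and f = 0.5 give −0.5 × (−0.3)/2 = +0.075.

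**Between arms.** Allocation is 1:1:1, so the expected difference in f is zero. For chance imbalance, take 75 subjects split at random into 25 per arm, with K early enrollees and p = K/75. The SD of the shift is (|δ|/2)·√[(1/25 + 1/25)·(75/74)·p(1−p)]:

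- K = 8: 0.044|δ|
- K = 19: 0.062|δ|
- K = 38: 0.071|δ|
- K = 56: 0.062|δ|
- K = 68: 0.041|δ|

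Simulation gave the same values. The central 95% range was widest at K = 38, at ±0.14|δ|.

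**Precision.** If all single values have equal, independent within-subject variance σ², the variance of a change is 2σ² with one baseline sample and 1.5σ² with two. The SD ratio is √(1.5/2) = 0.87, so the two groups differ in precision even when δ = 0.

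**The case against.** A reader might infer more: that the OBV value is suppressed by intravenous insulin, that this lowers the early enrollees' baseline, and that a false rise then appears on treatment. The documents do not support that chain.

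- No OBV or Day 1 value is given.
- An admission sample would come before the infusion.
- The infusion is not simply extra insulin. It replaces the pump, or the night-time basal dose withheld that evening. It starts at one half, one quarter or one eighth of the standard algorithm, according to regimen. Only subjects on morning basal insulin have it on top of a working basal dose.
- The 90–120 mg/dL target is close to the 80–120 mg/dL pre-breakfast target that all subjects follow from Day 1.

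A lower OBV value is plausible, but a higher one is not excluded. This objection stands in full against any claim about direction.

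It is also fair to say that SAP 10.1.1 allows stated exceptions, that the output is descriptive, that any shift would show in placebo too, and that the raw concentrations summarized by timepoint do not depend on the baseline rule. These points limit the consequence. They do not explain why one variable has two baselines within Part A. Cancellation against placebo helps only a reader who takes a between-arm difference, and 10.3.4.7 plans none.

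A last objection is that early enrollees repeat the overnight admission at Week 13, so an OBV-based baseline might match that visit better. As extracted, the Part A schedule could be read as placing a ketone sample on Day 85. The ketone row, however, has the same follow-up column pattern as the insulin diary row, which its footnote places at Weeks 16 and 20, and Part B shows those two visits for ketones. The objection is weak.

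**Conclusion.** The inconsistency is real and unexplained: within Part A, changes from baseline in serum ketones and free fatty acids pool two baseline definitions, and the rule averages only where the two samples were taken under unlike conditions. The difference in conditions holds on either reading of the OBV draw time. That Day 1 and weekly samples are fasted is read from their pairing with fasting glucose in Appendix A.

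The documents fix the form of the artefact, not its sign or size. It vanishes if δ = 0. A within-arm rise would need δ below zero, which nothing in the documents establishes, and even then it would be no treatment effect. The chance-imbalance figures assume 25 per arm and random allocation that does not balance enrolment before and after the amendment; the documents describe no such stratification. No hypothesis test is affected. This is a cheap improvement, not a threat to the trial's conclusions.

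**What to change.** In SAP 10.3.4.7, delete the averaging sentence and make the Day 1 pre-dose value, which is the 10.1.1 default of the last value before the first dose, the baseline for all subjects in both Parts. The artefact is then zero for any δ and f wherever the Day 1 sample exists. If it is missing, the default falls back on the earlier visit; flag those subjects in the listing.

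Keep the OBV value in the listings, or show the averaged version as a sensitivity summary. State the OBV draw time and the fasting and infusion status beside it.

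The cost is one sentence of SAP text before database lock, with no new data, because the sample is already scheduled. The downside is that early enrollees' baselines rest on one sample instead of two. Under the equal-variance assumption, the SD of their change rises by a factor of √(2/1.5) = 1.15, to the level that already applies to everyone else.
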